6.9.3 Use in Pregnancy

If a participant inadvertently becomes pregnant while on treatment with Pembrolizumab, the participant will immediately be removed from the study. The site will contact the participant at least monthly and document the participant's status until the pregnancy has been completed or terminated. The outcome of the pregnancy will be reported to the Sponsor, CI/delegate without delay and within 24 hours if the outcome is a SAE (e.g., death, abortion, congenital anomaly, or other disabling or life-threatening complication to the mother or newborn). The Sponsor, CI/delegate will notify MSD of all events within 48 hours. The PI will make every effort to obtain permission to follow the outcome of the pregnancy and report the condition of the fetus or newborn to the Sponsor, CI/delegate. If a male subject impregnates his female partner the study personnel at the site must be informed immediately and the pregnancy reported to the Sponsor, CI/delegate and followed as described above and in Section 7. If the pregnancy continues to term, the outcome (health of infant) must also be reported for up to 3 months.

6.9.4 Use in Nursing Women

It is unknown whether Pembrolizumab is excreted in human milk. Since many drugs are excreted in human milk, and because of the potential for serious adverse reactions in the nursing infant, participants who are breast-feeding are not eligible for enrolment.

6.10 Overdose of IMP

For purposes of this trial, an overdose of Pembrolizumab will be defined as any dose of 1,000 mg or greater (≥ 5 times the indicated dose). No specific information is available on the treatment of overdose of Pembrolizumab. Appropriate supportive treatment should be provided if clinically indicated. In the event of overdose, the participant should be observed closely for signs of toxicity. Appropriate supportive treatment should be provided if clinically indicated. Details of reporting an overdose can be seen in section 7.6.

6.11 Permanent Discontinuation of Study Treatment and Withdrawal from Study

6.11.1 Permanent discontinuation of study treatment

A participant must be discontinued from the trial for any of the following reasons:

- The participant withdraws consent.
- Confirmed radiographic disease progression

Note: For unconfirmed radiographic disease progression.

Note: A participant may be granted an exception to continue on treatment with confirmed radiographic progression if clinically stable or clinically improved. IMP will be provided off-study and as a special.

- Unacceptable AEs.
- Intercurrent illness that prevents further administration of IMP
- PI's decision to withdraw the participant
- The participant becomes pregnant
- Noncompliance with trial treatment or procedure requirements
- Administrative reasons

Trial participants will not be replaced once completing 21 days of treatment or enrolled more than once. The primary reason for discontinuation should be recorded. Once the trial medication has been discontinued the participant should complete the end of treatment and safety follow-up visit procedures as listed in the schedule of study assessments (Table 3). After the end of treatment, participants will continue to be assessed for AE and SAE monitoring until the SFU visit.

Participants will continue onto follow-up after the safety follow up, their details will be reviewed every 8 weeks \pm 7 days for details of disease status, initiating a non-study cancer treatment, withdrawing consent or becoming lost to follow-up. Follow-up will continue until the last participant has completed treatment or comes off study for disease progression or unacceptable toxicities.

6.11.2 Withdrawal from Study

Withdrawal from the study refers to discontinuation of IMP and study procedures and can occur for the following reasons:

- Participant decision
- Loss to follow-up
- Death
- PI/delegate Decision

Participants may withdraw consent at any time for any reason or be dropped from the trial at the discretion of the PI/delegate should any untoward effect occur. In addition, a participant may be withdrawn by the PI/delegate or the Sponsor if enrolment into the trial is inappropriate, the trial plan is violated, or for administrative and/or other safety reasons. Specific details regarding discontinuation or withdrawal are provided in below.

6.11.3 Procedures for Withdrawal from Study

When a participant withdraws prior to trial completion, all applicable activities scheduled for the final trial visit should be performed at the time of discontinuation. Any AEs which are present at the time of withdrawal should be followed in accordance with the safety requirements outlined in Section 7

6.12 Non-IMP details

Trans-arterial chemoembolization will be performed as a background treatment and as such is classed as a NIMP for the purpose of this study

7.0 PHARMACOVIGILANCE

7.1 Adverse Event (AE)

An AE is defined as any untoward medical occurrence in a participant administered a medicinal product and which does not necessarily have a causal relationship with this treatment. An AE can therefore be any unfavourable and unintended sign (including an abnormal laboratory finding), symptom, or disease temporally associated with the use of the IMP, whether or not considered related to the IMP.

Any worsening (i.e. any clinically significant adverse change in frequency and/or intensity) of a pre-existing condition that is temporally associated with the use of the Pembrolizumab and/or radiotherapy, is also an AE.

Changes resulting from normal growth and development that do not vary significantly in frequency or severity from expected levels are not to be considered AEs.

7.1.1 Disease Progression

Disease progression of the cancer under study is not considered an AE unless the investigator deems that it is at least possibly related to the Pembrolizumab.

7.1.2 New Cancers

The development of a new cancer should be regarded as an SAE and reported accordingly.

7.1.3 Abnormal Laboratory Test Results

All clinically significant abnormal laboratory test results occurring during the study will be recorded as AEs from after first administration of the IMP until for at least 30 days following the last dose of IMP or the discontinuation visit; whichever is the sooner. The clinically significant abnormal laboratory tests will be repeated at appropriate intervals until they return either to baseline or to a level deemed acceptable by the PI/delegate, or until a diagnosis that explains them is made.

Note: AEs seen at screening should be recorded as part of the participant's medical history.

7.1.4 Pregnancy and Lactation

Pregnancy and lactation are not considered AEs, however these events should be reported to the CI/delegate and subsequently to the Sponsor following guidance in below section.

7.2 Adverse Event recording

All AEs will be recorded from the time of signing the consent form and will be followed up for up to 130 days following the last dose of IMP. All adverse events will be recorded in the electronic Case Report Form (eCRF).

Any unresolved AEs at the participant's last visit should be followed up for as long as medically indicated, but without further recording in the eCRF.

If a PI/delegate learns of any SAEs, including death, at any time after a participant has completed the study and he/she considers there is a reasonable possibility that the event is related to Pembrolizumab, the PI/delegate should notify the Sponsor and CI/delegate

The following details will be collected for each AE:

- AE description / diagnosis
- Date and time of onset and resolution (if applicable)
- NCI-CTCAE grade (including any changes)
- Seriousness
- PI/delegate causality rating against the IMP
- Action taken with regard to IMP
- Outcome

7.2.1 Evaluating Adverse Events

AEs will be evaluated by a medically qualified physician.

7.2.1.1 Determining AE Severity and Grade

AE severity and grade will be evaluated according to the NCI CTCAE version 4.0. Any AE which changes CTCAE grade over the course of a given episode should be closed at the date and time the severity changed and a new AE recorded from the date and time of the new NCI CTCAE grade.

Grade 1	Mild; asymptomatic or mild symptoms; clinical or diagnostic observations only; intervention not indicated.
Grade 2	Moderate; minimal, local or non-invasive intervention indicated; limiting age-appropriate instrumental ADL.
Grade 3	Severe or medically significant but not immediately life-threatening; hospitalisation or prolongation of hospitalisation indicated; disabling; limiting self-care ADL.
Grade 4	Life threatening consequences; urgent intervention indicated.
Grade 5	Death related to AE

7.2.1.2 Determining AE Causality

The PI/delegate must endeavour to obtain sufficient information to determine the causality of the AE (i.e. IMP, other illness, progressive malignancy etc.) and must provide his/her opinion of the causal relationship between each AE and the IMP. This may require instituting supplementary investigations of significant AEs based on their clinical judgement of the likely causative factors and/or include seeking a further opinion from a specialist in the field of the AE.

Causality is the relationship of an AE to the IMP and will be determined as follows.

Definite:	
• There is clear evidence to suggest a causal relationship and other possible contributing factors can be ruled out.
Probable:	
• There is evidence to suggest a causal relationship and the influence of other factors is unlikely
Possible:	
• There is some evidence to suggest a causal relationship (e.g. because the event occurs within a reasonable time after IMP administration. However, the influence of other factors may have contributed to the event (e.g. the participant's clinical condition, other concomitant treatments)).
Unlikely:	
• There is little evidence to suggest there is a causal relationship (e.g. the event did not occur within a reasonable time after administration of the trial medication). There is another reasonable explanation for the event (e.g. the participant's clinical condition, other concomitant treatment).
Not related:	
• No evidence of any causal relationship.
Not assessable:	
• There is insufficient or incomplete evidence to make a clinical judgement of the causal relationships

Table 11: Assessment of Causality between AE and exposure to the IMP.

7.2.2 Reporting of Pregnancy and Lactation

It is the responsibility of PI/delegate to report any pregnancy or lactation in a participant (spontaneously reported to them), including the pregnancy of a male participant's female partner that occurs during the trial or 30 days following cessation of treatment if the participant initiates new anticancer therapy, whichever is earlier. All participants and female partners of male participants who become pregnant must be followed to the completion/termination of the pregnancy. Pregnancy outcomes of spontaneous abortion, missed abortion, benign hydatidiform mole, blighted ovum, fetal death, intrauterine death, miscarriage and stillbirth must be reported as SAEs. Consent to report information regarding these pregnancy outcomes from female partners of any males who took IMP will be obtained from the mother. If the pregnancy continues to term, the outcome (health of infant) must also be reported for up to 3 months.

Such events must be reported within 24 hours of learning of its occurrence to the Sponsor and CI/delegate who will subsequently inform MSD.

7.3 Serious Adverse Events (SAE)

7.3.1 Definition of SAE

An SAE is an AE occurring during any part of the study that meets one or more of the following criteria:

- Results in death;
- Is life threatening; or places the participant, in the view of the PI/delegate, at immediate risk of death from the event as it occurred¹

- Results in persistent or significant disability/incapacity;
- Results in or prolongs an existing inpatient hospitalisation²;
- Is a congenital anomaly/birth defect(in offspring of participant taking the product regardless of time to diagnosis);
- Is a new cancer (that is not a condition of the study);
- Is associated with an overdose (whether accidental or intentional). Any AE associated with an overdose is considered a SAE.
- Is an important medical event that may not result in death, not be life threatening, or not require hospitalisation but may be considered a serious adverse event when, based upon appropriate medical judgment, the event may jeopardise the participant and require medical or surgical intervention to prevent such an outcome.

¹ *This does not include an AE which hypothetically might have caused death if had it occurred in a more severe form.*

² *Hospitalisation is defined as an unexpected inpatient admission, regardless of length of stay, even if the hospitalisation is a precautionary measure for continued observation. It does not usually apply to scheduled admissions that were planned before study inclusion or visits to causality (without admission).*

7.4.1 Reporting of SAEs

Any SAE whether or not related to Pembrolizumab, occurring from informed consent until 130 days following cessation of treatment, or the initiation of new anti-cancer therapy, whichever is earlier, must be reported on an SAE report form within 24 hours of the PI or designee becoming aware of the event to the Sponsor and CI/delegate who will then inform MSD.

Please find below Sponsor details:

Imperial College Joint Research Compliance Office
Email address: [contact]

All SAEs regardless of causality, pregnancy or overdose should be documented and each episode of an SAE must be recorded on a separate SAE report form. The NCI CTCAE Version 4 must be used to grade each SAE, and the worsening of the grade is to be recorded.

If new or amended information on a previously reported SAE becomes available, the PI or delegate should update the SAE and report this to the Sponsor, CI/delegate. Follow up information about a previously reported SAE must be reported within 24 hours of receiving it. If the SAE has not been reported within the specified timeframes, a reason for lateness must be included when sending the SAE.

Additionally, any SAE, considered by a PI/delegate who is a qualified physician to be related to Pembrolizumab that is brought to the attention of the PI at any time outside of the time period specified in the previous paragraph also must be reported immediately to the Sponsor and CI. The CI/delegate will then inform the MSD.

These AEs will be followed up until resolved or stabilised at a level acceptable to the CI even if this is after the study reporting period.

7.4.2 Events exempt from being reported as SAEs

Events specified in this section do not require reporting as SAEs in this trial, unless hospitalisation is prolonged for any reason and then an SAE form must be completed. The events must still be recorded.

1. Elective admissions to hospital for procedures which were planned and documented in the medical records at the time of consent are not SAEs, and do not require SAE reporting.
2. Hospitalisation for administration of the IMP, or to facilitate study procedures according to the trial protocol, is also exempt from being reported as an SAE.

7.4.3 Determining SAE Causality and Expectedness

Assessment of causality and expectedness for all SAEs will be made by the PI/designee against the current approved version of the IB. If updated versions of the IB are released during the course of the trial then assessment of expectedness will be made against the current regulatory approved version.

7.5 Reporting of ECIs

Any ECIs whether or not related to the Pembrolizumab, occurring from the first dose until 30 days following the last treatment dose, or the initiation of a new anticancer therapy, whichever is earlier, must be recorded on the AE log and reported using the eCRF report form within 24 hours of the PI/designee becoming aware of the event to the CI or delegate who will then inform MSD.

7.6 Reporting of an Overdose

In the event of overdose, Pembrolizumab should be discontinued and the participant should be observed closely for signs of toxicity. Appropriate supportive treatment should be provided if clinically indicated.

If an AE(s) is associated with (“results from”) the overdose of Pembrolizumab, the AE(s) should be recorded on the AE eCRF and reported as a SAE, even if no other seriousness criteria are met.

If an overdose is taken without any associated clinical symptoms or abnormal laboratory results, the overdose is again recorded as an AE on the eCRF and reported as a non-serious ECI, using the terminology “accidental or intentional overdose without adverse effect.”

All reports of overdose either SAE or ECI must be reported within 24 hours of the PI/ designee becoming aware of the event to the Sponsor, CI/delegate by email who will inform MSD.

7.7 Definition of a Serious Adverse Reaction (SAR)

A SAR is defined as a SAE that is judged to be related to any dose of the IMP administered to the participant.

7.8 Definition of Suspected Unexpected Serious Adverse Reaction (SUSAR)

Any SAR that is NOT consistent with the applicable product information as set out in the IB.

7.9 Reporting of SUSARs

The Investigator and local study team will report all SUSARs to the Sponsor, CI/delegate within 24 hours of becoming aware of the event.

The Sponsor, CI/delegate will ensure that SUSARs are notified to the appropriate regulatory authority, the relevant Independent Research Ethics Committee (REC), MSD and the participating PIs in accordance with regulatory requirements and within the timelines specified in legislation (SI 2004/1031 as amended).

The Sponsor has delegated the responsibility for notifying the MHRA and REC of all SUSARs occurring during the study to the CI/delegate. All SAEs and SUSARs must be reported in accordance with local regulatory guidelines:

*Life threatening SUSARs should be reported to the MHRA and REC no later than **7 days** after the CI has first knowledge of the minimum criteria for expedited reporting. Further relevant information should be given within a further 8 days.*

*Non-fatal and non-life threatening SUSARs should be reported to the MHRA and REC no later than **15 days** after the CI has first knowledge of the minimum criteria for expedited reporting. Further relevant information should be given as soon as possible.*

Follow up of participants who have experienced a SUSAR should continue until recovery is complete or the condition has stabilised.

7.10 Annual Reporting of Serious Adverse Events

Annual reports will be submitted to regulatory authorities and REC by the CI or delegate in accordance with all applicable global laws and regulations. Copies will be forwarded to the Sponsor.

8.0 STATISTICAL ANALYSES

8.1 Sample Size and power considerations

Since this is the first time that Pembrolizumab is given to participants with chronic viral infection and limited functional liver reserve, we designed the study as a safety-oriented trial and considered enrolling a subsequent cohort of up to 26 participants following an initial safety run-in of 6 subjects to: 1) satisfy the safety aims of the study; 2) preliminarily document the efficacy of treatment to inform subsequent efficacy-testing in a future adequately powered trial; 3) obtain adequate information regarding the disease-modulating effects from treatment reflected by the proposed translational endpoints.

With primary endpoints being safety, no power calculation for hypothesis testing is required to formally power the study: the upper 95% confidence interval for toxicity events will inform the decision to proceed to a future, adequately powered phase II trial. Using the rule of three, if zero events are observed in 26 participants the upper 95% confidence interval will be 15%.

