In the Pembrolizumab monotherapy trials, in general, the most commonly reported Adverse Events (AEs) included fatigue, diarrhoea, decreased appetite, nausea, dyspnoea, and anaemia. The incidence of drug-related AEs (DRAEs) ranged from 39.8% (35 of 88 subjects in P013) to 80.0% (8 of 10 subjects in P011). The incidence of Grade 3-5 DRAEs across studies ranged from 6.8% (6 of 88 in P013) to 12.0% (187 of 1562 subjects) in P001/P002.

The most commonly reported Grade 3-5 DRAEs were anaemia, alanine aminotransferase (ALT) increased, aspartate aminotransferase (AST) increased, and colitis.

The majority of subjects who experienced an AE continued in the study, with the incidence of AEs leading to discontinuation ranging from 4.2% (18 of 430 subjects in P028) to 12.3% (192 of 1562 subjects in P001/P002). The majority of AEs leading to discontinuation were not considered drug related. Discontinuations due to a DRAE were infrequent and ranged from 0% (no subjects in P011) to 4.5% (4 of 88 subjects in P013). The most commonly reported DRAE leading to discontinuation was pneumonitis.

Hepatotoxicity, a clinically important safety concern in this study, is overall infrequent as a Pembrolizumab-related AE. Out of a total of 1562 subjects with advanced malignancies treated with Pembrolizumab monotherapy across a wide range of clinical trials, hepatic, drug-related autoimmune toxicity was identified in 8 subjects (0.5%), with 2 subjects qualifying for grade 3 toxicity (0.1%). Data from the use of Pembrolizumab in other indications, in absence of background hepatic impairment, suggest that liver toxicity did not appear to be a dose-dependent, but rather a stochastic immune-related AE. Management with oral corticosteroids for a median duration of 7 days has proven beneficial to antagonise this AE.

Efficacy data are available for a total of 655 P001 melanoma subjects treated with Pembrolizumab and 540 P002 melanoma subjects treated with either Pembrolizumab or chemotherapy. For both clinical studies, assessment of overall response rate (ORR) was based on RECIST 1.1 and performed by blinded central reviewers.

The P001 ORR demonstrated the antitumour activity of Pembrolizumab in subjects with melanoma (ipilimumab-naïve and previously treated with ipilimumab).

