3.0 STUDY DESIGN

3.1 Design

The study will be performed at 1-4 sites in the UK and will recruit up to a maximum of 32 evaluable participants. This study is an OL, single arm, sequential phase study evaluating safety, tolerability and preliminary efficacy of sequential TACE followed by Pembrolizumab and will be conducted in two parts.

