3.1.2 Part Two

Once the data for 6 patients are reviewed by the IDSMC in part 1 a further 26 evaluable participants will be recruited to the study with the same regimen - TACE followed by 200 mg Pembrolizumab after at least 30

days window or with TACE followed by 200 mg after at least 45 days. This will further characterise the safety and tolerability of Pembrolizumab in this population.

In this part of the study, if a participant withdraws or is withdrawn from the study prior to completion of the first 21 day treatment period, in the absence of a DLT, that participant must be replaced. If a participant is withdrawn for any reason before receiving Pembrolizumab, replacement with an additional participant will be allowed.

Participants entering part two of the study must be assessed up to 28 days prior to TACE to confirm eligibility and be recruited onto the trial. They will be scheduled for Pembrolizumab dosing as per agreed time window determined by IDSMC and will be given Pembrolizumab every Q3W \pm 3 days until radiologically confirmed disease progression, unacceptable toxicity, withdrawal or a maximum of 1 year of treatment has been completed.

If the pembrolizumab dosing scheduled is set at 45 days after TACE, at least 1 participant will be mandated to meet Child-Pugh B7 criteria in the safety run-in phase to ensure wide generalisability of the safety outcomes to the full spectrum of severity of background liver dysfunction.

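### Section 8.1 gives 15% as the rule-of-three upper limit for 0 of 26 events, but the rule gives 3/26 = 11.5%

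*Combined protocol and SAP*

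**What the plan says.** Section 8.1 states that no power calculation is needed because the primary endpoint is safety. In its place, "the upper 95% confidence interval for toxicity events will inform the decision to proceed to a future, adequately powered phase II trial". The section then illustrates the planned precision: "Using the rule of three, if zero events are observed in 26 participants the upper 95% confidence interval will be 15" (per cent).

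The 26 is the expansion cohort. Section 8.1 describes "a subsequent cohort of up to 26 participants following an initial safety run-in of 6 subjects", section 3.1.2 says that "a further 26 evaluable participants will be recruited to the study" after Part 1, and Table 1 in section 3.2 lists 26 for Part 2. Section 3.1 gives the total: the study "will recruit up to a maximum of 32 evaluable participants".

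Section 8.3 puts everyone who receives at least one dose into the safety analysis set. It promises 95% confidence intervals for all estimates, but names no interval method and does not say whether the limits are one-sided or two-sided.

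**The concern.** One sentence names the method, the event count and the sample size, so its result can be checked directly, and the stated result does not follow. No table, figure or blacked-out text is involved, and n = 26 agrees with sections 3.1.2 and 3.2, so a misprinted n is an unlikely explanation.

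The stake is modest. This is the only numerical statement of precision for the primary endpoint. An ethics committee member, an IDSMC member or a phase II planner who repeats the calculation will get a different answer and will not know whether the method, the n or the result is wrong. A 15% limit also makes a zero-event result look less informative than it would be.

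**Working it through.** **Inputs.** Method: rule of three. Events: 0. n = 26. Level: 95% upper limit, sidedness not stated. All are from section 8.1. The alternative n of 32 is from section 3.1.

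**The plan's own figure.** With no events in n participants, the rule of three puts the upper limit at 3/n. It approximates a one-sided 95% bound because −ln(0.05) is close to 3.

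- 3/26 = 0.1154, or 11.5%.
- Stated: 15%. Difference: 15 − 11.5 = 3.5 percentage points.

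The stated figure is not reproduced.

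**Other 95% limits for 0/26.**

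| Method | Calculation | Upper limit |
|---|---|---|
| Exact, one-sided | 1 − 0.05^(1/26) | 10.9% |
| Wilson, two-sided | 3.84/(26 + 3.84) | 12.9% |
| Exact (Clopper-Pearson), two-sided | 1 − 0.025^(1/26) | 13.2% |
| Two-sided analogue of the rule | −ln(0.025)/26 | 14.2% |
| Agresti-Coull, adding 2 events and 4 participants | 2/30 + 1.96 × √[(2/30)(28/30)/30] | 15.6% |
| Agresti-Coull, adding z²/2 and z² (z = 1.96) | 1.92/29.84 = 0.0644; 0.0644 + 1.96 × √(0.0644 × 0.9356/29.84) | 15.2% |

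Only the last rounds to 15%. It is a different method from the one named and lies above the exact limit here, and nothing in the documents suggests it was used.

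**Other values of n.** With all 32 evaluable participants the rule gives 3/32 = 9.4%, further from 15%. It gives 15% at n = 3/0.15 = 20. The documents do not say where the 15% came from.

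**Confidence attached to each figure at 0/26.**

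- 15%: 1 − 0.85^26 = 1 − 0.0146 = 98.5% one-sided.
- 11.5%: 1 − (1 − 3/26)^26 = 1 − 0.0413 = 95.9% one-sided.
- The upper end of a two-sided 95% interval is a 97.5% one-sided bound, so 15% exceeds that too.

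**When the count is not zero.** The rule of three applies only to zero events. Section 8.1 does not define the toxicity event, so the chance of seeing at least one in 26 depends on an assumed rate p, as 1 − (1 − p)^26. Section 1.2.2 gives several monotherapy rates from other populations:

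- Grade 3–5 drug-related events, 6.8% to 12.0%: 1 − 0.932^26 = 84.0% and 1 − 0.88^26 = 96.4%.
- Drug-related autoimmune hepatic toxicity, 0.5%: 1 − 0.995^26 = 12.2%.
- The same at grade 3, 0.1%: 1 − 0.999^26 = 2.6%.

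The chance of needing a method other than the rule of three therefore runs from about 3% to 96%, depending on the event chosen. For one event in 26, the exact upper limit would be 17.0% one-sided or 19.6% two-sided.

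**The case against.** The best defence is that this is a planning illustration with no consequence. The Part 1 decisions rest on DLT counts (sections 3.1.1 and 6.5). Section 8.1 sets no cut-off for phase II, and the limit used then will come from the observed data. The error is also in the cautious direction. All of this stands, and it keeps the point minor, but it does not make the figure correct.

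If a two-sided interval was meant, as the wording of section 8.3 suggests, the gap is smaller: 15% against an exact 13.2%, or 1.8 points. That is fair as to size. The sentence still names a rule that gives 11.5%.

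The method for non-zero counts is a separate matter. Section 8.1 invokes the rule only for zero events, and section 8.3 already promises confidence intervals. This also stands: what is missing is the name of the interval method, and asking for it is a clarification rather than part of the arithmetic error.

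Finally, the safety set in section 8.3 is everyone dosed, in both parts, so 26 may not be the n that matters. This is a fair point for the sponsor to settle, but the larger n moves the limit down to 9.4% and does not rescue 15%.

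**Conclusion.** The concern holds. From the method, count and n stated in section 8.1, the upper limit is 11.5%, not 15%, an overstatement of 3.5 percentage points. If the method were changed to the exact two-sided 95% interval, the overstatement would be 1.8 points.

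The conclusion uses only the inputs in that sentence and needs no outside assumption. The chances of a non-zero count rest on assumed event rates and are not needed for it.

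Severity is minor. Planned precision at zero events is better than the protocol says, and the error affects no participant, decision rule or sample size.

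**What to change.** In section 8.1, do one of the following:

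- Keep the rule of three and replace 15% with 11.5%, described as an approximate one-sided 95% bound (exact one-sided value 10.9%).
- If a two-sided interval is intended, replace both the method and the figure: exact (Clopper-Pearson) two-sided 95% upper limit, 13.2%.

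In the same edit, say whether the bound describes the Part 2 cohort of 26 or all dosed participants. At 32, the rule of three gives 9.4% and the exact two-sided limit is 1 − 0.025^(1/32) = 10.9%.

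As an optional clarification, add that toxicity proportions will be reported with exact binomial limits of the same sidedness, so that a method is named if any event occurs.

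The cost is one or two sentences. No further participants or data are needed, and no analyses beyond the intervals already promised in section 8.3.
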